To determine bacteria in the infant's mouth which may originate from the mother's breast milk or donor milk, a small sample of breast milk (3-5 mL) will be obtained from the infant's mother (after her consent) at the end of week 1 and 4 and 16S rRNA sequencing will be performed. Samples will be obtained from the NICU milk room. If mother is pumping < 5mL/, no sample will be obtained but no deviation reported. If donor breast milk is used for oral care (mother is not providing breast milk to her infant), 3-5 mL of donor breast milk will be obtained and 16s rRNA sequencing performed

Aim 2: will compare respiratory outcomes including evidence of VAP (positive ETT culture, incidence of ventilator associated events), days on invasive and non-invasive respiratory support, and incidence of BPD between groups. We hypothesize that infants who undergo standardized oral care every 3-4 hours will have less VAP, require fewer days of respiratory support, and have less BPD than Group 2. Descriptive statistics, including confidence intervals, will be generated to describe the distribution of days of respiratory support in each group, and measures of effect size (Cohen's *f*) will be calculated from the between-subjects (Treatment Group, with 3 levels) general linear model (GLM). Incidence of occurrence for VAP and BPD will be described for each group using frequencies and percentages along with confidence intervals for the proportions. Effect sizes (Cohen's *w*) for each of those two outcome variables will be calculated from a 3 (Treatment) by 2 (Occurrence) contingency table.¹⁹

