Information concerning infant demographics and health outcomes will be collected from the infant's electronic health records. Traditionally, VAP has been diagnosed using radiographic evidence of pneumonia. However, radiographs have not been shown to be a valid or reliable method of diagnosis especially in neonates who often have underlying lung disease making radiographic diagnosis even more difficult. Therefore, in accordance with the National Healthcare Safety Network 2021 recommendations for neonatal and pediatric patients, VAP will be defined as the incidence of ventilator associated events (VAE).¹ VAEs are objectively defined events consisting of deterioration in respiratory status after a period of stability or improvement in ventilated infants. VAEs occur when a ventilated infant has either an increase in daily minimum oxygen requirement of ≥ 0.25 or mean airway pressure of ≥ 4 cm sustained for more than 2 days after more than 2 days of stable or decreasing daily minimum oxygen level or mean airway pressure.

If the infant is ventilated with an endotracheal tube, a weekly (for 4-weeks) culture and gram stains will be obtained from the endotracheal tube and sent to the laboratory for analysis to assess for bacteria which may be in the infant's airway. This ETT culture will be obtained with assistance by the infant's nurse or respiratory therapist when suctioning was to occur as part of routine care. The culture and gram stain will be sent to UF Shands Laboratory. Furthermore, days on respiratory support (ventilation, continuous positive airway pressure, high flow nasal cannula or low flow nasal cannula), incidence of BPD (oxygen requirement at 28 days of life), and length of hospital stay will be collected during the infant's NICU stay. Other clinical information which could potentially affect the risk of oral secretion aspiration will be collected including days requiring sedation, days of antibiotic therapy, and number of intubations.⁶

All de-identified saliva, stool and breast milk samples will be conducted at a UF lab outside of Shands. No EPIC charges apply, as these are being directly paid to the lab by research funds. ETT culture samples will also be de-identified before sending to Shands CoreLab. There will be no EPIC orders and no results of culture will be placed in EPIC. Core lab services are being set up as a direct pay.

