1. Presence of bacteria in the infant's breathing tube	Presence of positive tracheal aspirate on ventilated infants	Weekly for 4 weeks
2. Respiratory Support	Days of invasive and non-invasive respiratory support.	Day of birth until NICU discharge
3. Evidence of pneumonia	Episodes of radiologic evidence of pneumonia	Day of birth until NICU discharge
Analysis of stool (1-2)		
1. Microbial analysis	16S rRNA and metagenomics sequencing	End of week 1 & 4
2. Inflammatory markers	Analysis of inflammatory markers	End of week 1 & 4
Nutritional outcomes (1-6) below		
1. Enteral intake	24-hour enteral feeding intake in mL/kg and calories, episodes of emesis, # of oral colostrum buccal swabs received	Day of birth until discharge from the NICU.
2. Time to full feeds	First day infant received 120 mL/kg/d and 150 ml/kg/d of feedings	Recorded daily until 150 mL/kg/d reached
3. Hours of parenteral nutrition	Number of hours infant received some parenteral nutrition	Daily until NICU discharge

4. Parenteral nutrition associated liver disease	Liver function tests (level of direct bilirubin, alkaline phosphatase, AST and ALT)	Weekly or biweekly until NICU discharge (with clinically sent labs)
5. Hours of central line access	Number of hours infant has a central line	Daily until NICU discharge
6. Growth indices	Weight, length, and head circumference	Daily (weight) and weekly (head circumference and length) until NICU discharge.
7. Length of time feeding and endotracheal tubes were in place	Hours tubes remained in place.	Daily for 5 weeks.
Other health outcomes (1-3) below		
1. Episodes of late onset sepsis	CBC lab results, episodes of culture proven or presumed sepsis (treated with ≥ 5 days of antibiotics but with negative cultures) occurring ≥ 3 days after birth	Daily from birth until NICU discharge
2. Episodes of necrotizing enterocolitis	Episodes of radiologic or surgical necrotizing enterocolitis	All incidents until NICU discharge
3. Discharge summary	Days infant remains in hospital, hospital course, subject diagnosis	From birth until discharge
Covariates		
1. Analysis of maternal breast milk (if mom pumping) and donor breast milk	Microbiota and metagenomic sequencing (3-5mls)	At the end of week 1 and 4
Oral Conditions		
1. Bacteria in saliva	Amount and type of bacteria in the mouth	Sputum samples weekly for 4 weeks
2. Examination of mouth	Assessment of skin integrity and presence of erythema, exudate or thrush.	3x a week for 5 weeks.

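### Aim 2 reads fewer raw days of respiratory support as benefit but plans nothing for death, so an early death on support improves its arm's mean

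*Protocol*

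**What the plan says.** Protocol section 6 (Research Plan), Aim 2, states the direction of benefit: infants given care every 3-4 hours are expected to "require fewer days of respiratory support, and have less BPD than Group 2". The analysis sentence reads "Descriptive statistics, including confidence intervals, will be generated to describe the distribution of days of respiratory support in each group". The effect size is Cohen's f from a general linear model with treatment group as a three-level factor, which is a contrast of arm means. For VAP and BPD the effect size, Cohen's w, "will be calculated from a 3 (Treatment) by 2 (Occurrence) contingency table".

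Table 1, row Respiratory Support, gives the measurement as "Days of invasive and non-invasive respiratory support" and its timing as "Day of birth until NICU discharge". The outcome definitions later in Aim 2 say "incidence of BPD (oxygen requirement at 28 days of life), and length of hospital stay will be collected" during the NICU stay.

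Two places come near to death. The exclusion criteria remove infants judged unlikely to survive past 7 days. The discharge summary row of Table 1 lists "Days infant remains in hospital, hospital course, subject diagnosis". Neither makes death an outcome, a data item or an event in the analysis.

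**The concern.** The protocol fixes the measure (a raw count to discharge), the favourable direction (fewer) and the model (arm means). Together these credit an early death. An infant who dies on support at two weeks contributes about 14 days and scores better than a survivor who needed 50. The distortion can run either way: an arm that prevented early deaths would accumulate support days and look worse.

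Deaths within the counting window are possible. The exclusion rests on expected survival to one week only, while the count runs to discharge.

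If the number or timing of deaths differs between arms, by effect or by chance, the arm means and Cohen's f mix survival with need for support. No planned table would let a reader see it. Aim 2 is descriptive in a self-described pilot, so what is at stake is a misleading effect estimate carried into later work rather than a wrong formal test.

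BPD raises a secondary point. It is a status at day 28, so it is undefined for an infant who dies earlier, and a table of occurred versus not occurred gives that infant no evident place. An SAP may settle that coding.

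**Working it through.** The protocol states no mortality, support-day, SD or BPD figure, so there is nothing to reproduce. From the protocol come 217 infants and three arms of comparable size, hence 217/3, about 72 per arm. Every other input is an assumption. Infants are treated as independent.

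**Support days.** With mortality m, survivors' mean S and mean D in infants who die, the arm mean is (1 − m)S + mD. Survivors are taken as alike in both arms.

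| S | D | m = 0.15 | m = 0.10 | Difference |
|---|---|---|---|---|
| 40 | 12 | 35.8 | 37.2 | −1.4 |
| 40 | 14 | 36.1 | 37.4 | −1.3 |
| 60 | 12 | 52.8 | 55.2 | −2.4 |
| 60 | 14 | 53.1 | 55.4 | −2.3 |
| 60 | 60 | 60.0 | 60.0 | 0 |
| 60 | 90 | 64.5 | 63.0 | +1.5 |

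- **Equal mortality, S = 50, D = 14 versus 34.** At m = 0.10 the means are 46.4 versus 48.4 (−2.0). At m = 0.15 they are 44.6 versus 47.6 (−3.0). With the same timing of death the difference is 0.
- **One survivor replaced by an early death.** The arm mean falls by (40 − 14)/72 = 0.36 to (60 − 12)/72 = 0.67 day.
- **A wider gap.** With mortality of 5%, 5% and 15%, S = 45, SD 25 and death at day 10, the means are 0.95 × 45 + 0.05 × 10 = 43.25 in two arms and 0.85 × 45 + 0.15 × 10 = 39.75 in the third. The arm with most deaths looks best by 3.5 days.

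**Size against noise.**

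- The 95% half-width for a difference of two arms is 1.96 × SD × √(2/72): 6.5 days at SD 20 and 9.8 at SD 30.
- If one of three equal arms is shifted by d, f = (√2/3) × d/SD = 0.4714 × d/SD. This gives 0.4714 × 1.3/30 = 0.020 to 0.4714 × 2.4/20 = 0.057.
- The root-mean-square f expected by chance is √(2/214) = 0.097.

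**BPD.** All deaths are placed before day 28, at 15% versus 10%.

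- **Deaths coded as not occurred, BPD in 50% or 70% of survivors in both arms.** 0.85 × 0.50 = 0.425 versus 0.90 × 0.50 = 0.450 (2.5 points less). 0.85 × 0.70 = 0.595 versus 0.90 × 0.70 = 0.630 (3.5 points less).
- **Deaths dropped and unrelated to BPD risk.** Difference 0.
- **Deaths dropped, every death a would-be BPD case, the same underlying risk of 0.55 or 0.73 in both arms.** (0.55 − 0.15)/0.85 = 0.471 versus (0.55 − 0.10)/0.90 = 0.500 (2.9 points less). (0.73 − 0.15)/0.85 = 0.682 versus (0.73 − 0.10)/0.90 = 0.700 (1.8 points less).
- **Half-width.** 1.96 × √(0.425 × 0.575/72 + 0.450 × 0.550/72) = 0.162, about 16 points.

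**The remedy under the same 15% versus 10%, survivors alike.**

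- Death-or-BPD: 0.15 + 0.85 × 0.50 = 0.575 versus 0.10 + 0.90 × 0.50 = 0.550, and 0.745 versus 0.730. The higher-mortality arm now shows 1.5 to 2.5 points more.
- Ranks with death worst: the chance that its infant ranks worse is 0.15 × 0.90 + 0.5 × 0.15 × 0.10 + 0.5 × 0.85 × 0.90 = 0.525, with half-width about 1.96 × √(145/(12 × 72²)) = 0.095.

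**The case against.** The strongest objection is that this belongs in an SAP. How deaths enter a duration summary, who forms the denominator and how an unobserved day-28 status is coded are often settled there, and the protocol never says that infants who die enter the model with a truncated count. That stands for the BPD coding. It does not dispose of support days, because measure, direction and model are already fixed in the protocol, and Table 1 would still lack a death field. Reading Aim 2 as survivors only would not rescue it either: that conditions on survival after randomisation and still shows no deaths.

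The second objection is size. Every input is assumed, the shift runs from 3.5 fewer days through zero to 1.5 more, nothing in the protocol predicts a difference in mortality, and the effects sit below chance scatter. This is right and sets the priority. It does not make the direction of the error acceptable.

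Third, deaths can be found in the health record or discharge summary, and the 7-day exclusion thins the earliest ones. Also right: what is missing is a named item, a reporting line and an analysis that does not reward early death.

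Fourth, the composite does not always show harm. In the case where every death is a would-be BPD case it gives 0.55 versus 0.55 and 0.73 versus 0.73. That is the proper answer when deaths replace BPD one for one, whereas dropping deaths shows a false gain of 1.8 to 2.9 points. The difference in mortality itself is then visible only if deaths are reported separately.

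**Conclusion.** The concern holds. As written, Aim 2 counts an early death on support as a favourable result, and no planned display would reveal it. At an assumed 15% versus 10% mortality with survivors alike, the false gain is 1.3 to 2.4 days (f of 0.02 to 0.06) when infants who die average 12 to 14 support days and survivors 40 to 60. It is zero when number and timing of deaths match across arms, and it reverses when deaths follow long support.

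The actual size cannot be known from the protocol, and the illustrated shifts are smaller than the pilot's likely imprecision. The case rests on direction and interpretability. It should be fixed, at minor to moderate priority, because the correction is cheap.

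**What to change.** 1. Add death and its date to Table 1 as a named outcome taken from the health record, and report deaths by arm beside every Aim 2 summary.
2. In the three-by-two table, report death before day 28 or oxygen requirement at day 28. Show death, and BPD among survivors, separately, each with its denominator.
3. Keep the planned raw-days model and Cohen's f, labelled as description, with days shown in survivors and in all infants. Add one pre-stated death-aware comparison, for example ranks with death before discharge as worst. Other death-aware methods would serve as well.

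The cost is one added data item, two derived variables and some wording. No planned analysis is removed. The composite mixes death with BPD, and ranks lose the scale in days, which is why the components and raw days stay alongside. The change corrects how deaths count but adds no precision: a result such as 52.5% with a half-width of about 9.5 points would not be distinguishable from 50%.

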In a national survey of 129 neonatal nurses from 35 states, we found that while over 98% stated oral care was important for the health of VLBW infants, less than 37% felt their NICU adequately addressed oral care. In addition, tremendous variation existed in practices regarding oral care including the method, timing, equipment and whether or not oral care was even performed.

5. Specific Aims:

The long-term goal of this research is to improve short and long-term health outcomes for premature very low birth weight (VLBW; <1500 grams) infants by decreasing complications caused by lack of frequent standardized oral care.

Specific aims are as follows:

Aim 1: To compare the oral microbiome between groups including bacterial pathogenicity determinants.

Aim 2: To compare respiratory outcomes including the incidence of ventilator associated pneumonia, bronchopulmonary dysplasia and need for respiratory support between groups.

6. Research Plan:

Sample and Setting:

The proposed study will prospectively follow 217 VLBW infants and 217 mothers (dyad) for 4 weeks following birth (includes 69 previously enrolled mother/infant dyads). Infants will be randomized into 1 of 3 groups. Standardized oral care will be performed every 3-4 hours (Group 1) and every 12 hours (Group 2) using sterile water. Group 3 will have standardized oral care performed every 3-4 hours using human milk (mother's breast milk or donor breast milk). Mothers of multiples will also be potential subjects. UF NICU nursing staff will receive UF Qualtrics survey links to their UF email yearly. Survey responses are voluntary and anonymous and will include up to 225 RN responses.

Infants will be sampled by convenience from the NICU at UF Health Shands Children's Hospital. Approximately 150 premature VLBW infants are admitted to this NICU per year. Our consent rate in similar studies is > 60% which strongly suggests we will be able to recruit 217 infants and 217 mothers (dyad) over a 12-month period.

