A yearly anonymous and voluntary survey will be administered to the NICU nursing staff using a UF Qualtrics link sent to their email regarding staff concerns and questions. An IRB approved waiver of consent, will be sent with each survey, with an expected response of 225 staff. Yearly Q & A sessions will be scheduled as needed for staff questions and/or concerns. To encourage protocol compliance, nurses will receive quarterly emails or flyers will be posted with study updates or information important to study compliance. New nurses will be

formally oriented to the study during their orientation period. We have previously successfully used these strategies.

Data Entry and Management

All data will be entered into REDCap by a research assistant and verified by a Research Coordinator. A unique identifier will be assigned to each enrolled participant that will serve as the unique subject ID. Personal Health Information will not be stored in the study database. The study case report forms (CRFs) will be maintained in study specific folders. The CRFs are considered the primary data collection instruments for this study. When CRFs are not actively being processed, they will be secured in locked file cabinets. In addition to the use of passwords and other security measures, all documents containing identifying information are considered confidential materials and are safeguarded to the greatest possible extent. No individually identifying information will be released or discussed with anyone other than study staff.

Table 1. Instruments

Variable	Measurement	Timing
Descriptive (1-2) below		
1. Maternal, prenatal and perinatal demographics	Data extracted from medical record: Maternal history, prenatal and perinatal complications and medications, mode of delivery, whether mother received antibiotics and/or antenatal steroids	Collected upon entry into study.
2. Infant demographics	Data extracted from medical record: Race/ethnicity, sex, gestational age, birth weight, Apgar scores, resuscitation at birth and neonatal acuity (SNAP II) score	Collected upon entry into study.
3. Infant data	Type and amount of feeding, whether or not the infant is NPO, number of days and type of antibiotics, whether the infant was diagnosed with oral thrush and type of treatment. Length of skin-to-skin care	Collect upon entry into study and until infant discharge
Respiratory Factors (1-2)		

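### Aim 2 hypothesises better outcomes than Group 2, but its only between-group measures are unsigned three-arm effect sizes, and no difference versus Group 2 with an interval is planned

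*Protocol*

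**What the plan says.** The hypothesis in section 6, Aim 2, is directional and names its comparator. Infants receiving care every 3-4 hours (Group 1 with sterile water, Group 3 with human milk) "will have less VAP, require fewer days of respiratory support, and have less BPD than Group 2", which is care every 12 hours with sterile water.

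The same paragraph then sets out the analysis:

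- **Days of respiratory support, summaries:** "Descriptive statistics, including confidence intervals, will be generated to describe the distribution of days of respiratory support in each group".
- **Days of respiratory support, between groups:** Cohen's f, which "will be calculated from the between-subjects (Treatment Group, with 3 levels) general linear model (GLM"). Treatment group is the only term stated.
- **VAP and BPD, summaries:** incidence "will be described for each group using frequencies and percentages along with confidence intervals for the proportions".
- **VAP and BPD, between groups:** Cohen's w, which "for each of those two outcome variables will be calculated from a 3 (Treatment) by 2 (Occurrence) contingency table".

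The protocol contains no difference or ratio against Group 2 for any Aim 2 outcome, and no interval for one. Its one method for comparing two groups, STAMP, belongs to the Aim 1 microbiome profiles.

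Two further statements bear on the remedy. Table 1 records at study entry "gestational age, birth weight, Apgar scores, resuscitation at birth and neonatal acuity (SNAP II) score". Under Sample and Setting, multiples are eligible: "Mothers of multiples will also be potential subjects".

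**The concern.** The question is about direction and about one particular arm. Cohen's f and w answer another question: how far the three arms spread around their overall average. Neither can be negative. With equal arm sizes neither changes when the arms are relabelled, so both take the same value whether Group 2 does worst (hypothesis supported) or best (hypothesis contradicted). Both are also above zero on average when treatment does nothing.

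The per-arm intervals do not fill the gap. They show direction informally but give no uncertainty for a difference, and overlap between two arm intervals is a poor guide to whether the arms differ.

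At stake is the main output of a pilot, an estimate with its uncertainty. The estimate that Aim 2 is about is not named, so a reader would have to build it from separate arm summaries, and the choice of contrast would be open after the data are seen.

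**Working it through.** The protocol gives no event rate, standard deviation, effect size or significance level for Aim 2, so there is no figure of its own to reproduce. The check is whether the planned quantities can carry the hypothesis.

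**Inputs.** From section 6: 217 infants, three arms of comparable size through blocked randomisation, taken here as 72, 72 and 73. All BPD counts and mean days below are assumed.

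**1. Values expected with no effect.** With N = 217 and 2 degrees of freedom:

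- E[w] = E[√(χ²₂/217)] = 0.085; 95th percentile √(5.99/217) = 0.166.
- E[f] = E[√(2F/214)] with F ~ F(2, 214) = 0.086.

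**2. A pattern that supports the hypothesis.** BPD in 25/72, 36/72 and 26/73, that is p₁ = 34.7%, p₂ = 50.0%, p₃ = 35.6%.

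- Wilson 95% intervals by arm: 24.8-46.2%, 38.7-61.3%, 25.6-47.1%. Those for Groups 1 and 3 each overlap Group 2's by about 7 to 8 points.
- Pearson χ² = 4.42, so w = √(4.42/217) = 0.143, below 0.166.
- Contrast (p₁ + p₃)/2 − p₂ = −0.148.
- SE = √[p₂q₂/72 + ¼(p₁q₁/72 + p₃q₃/73)] = √[0.00347 + ¼(0.00315 + 0.00314)] = 0.071.
- 95% CI: −28.8 to −0.9 percentage points.

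**3. The same w with other answers.**

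| BPD counts (Groups 1, 2, 3) | w | Average of Groups 1 and 3 minus Group 2, points (95% CI) |
|---|---|---|
| 25/72, 36/72, 26/73 | 0.143 | −14.8 (−28.8 to −0.9) |
| 47/72, 36/72, 47/73 | 0.143 | +14.8 (0.9 to 28.8) |
| 36/72, 25/72, 26/73 | 0.143 | +8.1 (−5.5 to 21.7) |

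**4. Relabelling in general (equal arms).** Rates of 30%, 38% and 45% give w = 0.1265 under all six assignments to the arms, while the contrast runs from −11.0 to +11.5 points. Mean days of 18, 20 and 24 with SD 12 give f = 0.208 under all six, while the contrast runs from −5 to +4 days.

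**5. What the missing estimate would deliver.** With 217/3 = 72.3 per arm, and ignoring clustering and dropout, the 95% half-widths at a common event rate p are:

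- One arm versus Group 2, 1.96√(2p(1−p)/72.3): ±9.8 points at 10%, ±14.9 at 30%, ±16.3 at 50%.
- Groups 1 and 3 versus Group 2, 1.96√(1.5p(1−p)/72.3): ±8.5, ±12.9 and ±14.1 points.
- Mean days: ±0.33 SD and ±0.28 SD respectively.

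**6. Gain from baseline adjustment.** It depends on prognostic strength, which the protocol does not give.

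- For days, the interval narrows by 1 − √(1 − R²): 5% at R² = 0.1 and 29% at R² = 0.5.
- For a standardised BPD risk difference, simulation with one normal baseline covariate (1500 trials per setting) gave a narrowing of 2%, 5%, 10% and 18% at baseline AUC of 0.63, 0.70, 0.77 and 0.84.

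**The case against.** **A separate SAP may add contrasts.** Contrasts, covariates and clustered errors are usual SAP content, and a three-level linear model yields pairwise differences directly. This stands as a limit: the absence is shown for the protocol only. It does not remove the point, because the protocol is not silent. It states an analysis, and an SAP that followed it faithfully would inherit the mismatch.

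**Direction can be read from the arm percentages.** True, and the frequencies would let a reader compute the difference. What is missing is a named contrast, fixed in advance, with its own interval.

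**This is a pilot with no planned test, and f and w can help size a later trial.** That explains an estimation approach, but not the choice of omnibus indices over the estimate of interest. The 0.166 value is a yardstick for chance variation, not a test the protocol plans.

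**The illustration is invented and close to the margin.** This stands. On the same counts Group 1 minus Group 2 is −15.3 points (−31.2 to +0.7) and Group 3 minus Group 2 is −14.4 (−30.3 to +1.6). The combined contrast would include zero if its variance were about 1.13 times larger. Clustering need not inflate the variance when infants are individually randomised. In any case the argument rests on w being the same for benefit and harm, which does not depend on where one interval ends.

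**An unadjusted analysis is valid under randomisation.** Correct. Adjustment is a lesser, precision-only part of the point.

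**Conclusion.** The concern holds. Aim 2 poses a directional comparison with Group 2, and the analysis stated for it does not estimate that comparison. The same w of 0.143 accompanies a contrast of −14.8, +14.8 or +8.1 points, depending only on which arms have the events. In the first of these patterns the planned outputs look unremarkable although the interval for the hypothesised contrast excludes zero.

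The structural conclusion needs no assumption beyond the protocol's text. The sizes rest on assumed BPD counts, near-equal arms of about 72, and no allowance for clustering or dropout. The gain from adjustment rests on assumed prognostic strength and may be small. This should be fixed; it is a defect in what will be reported and does not invalidate the design.

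**What to change.** For each Aim 2 outcome, pre-specify two contrasts: (a) the average of Groups 1 and 3 versus Group 2, which is the hypothesis as written, and (b) Group 1 versus Group 2, which isolates frequency with the same fluid. Report each as a mean difference (days) or risk difference (VAP, BPD) with a 95% confidence interval.

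Estimate them from a model with treatment group, gestational age, birth weight and SNAP II: linear for days, and logistic for VAP and BPD with risk differences obtained by standardisation. Use standard errors clustered by mother, since multiples are eligible. If VAP events are too few for the logistic model, report the unadjusted risk difference with its interval. Keep the per-arm summaries, and keep f and w as supplementary.

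The cost is a few sentences in the protocol or SAP and a few lines of code, with no new data. The contrasts and model must be fixed before outcomes are examined by arm, including those of the 69 dyads already enrolled.
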